7.1 General Study Design

This Phase 2, multi-center, double-masked, randomized, placebo-controlled, dose-ranging, study is designed to evaluate the clinical efficacy and safety of RTA 408 Ophthalmic Suspension 0.5% and RTA 408 Ophthalmic Suspension 1.0% compared to placebo in patients following ocular surgery. Approximately 105 male and female patients at least 18 years of age undergoing unilateral cataract extraction via phacoemulsification in one eye and meeting all other study eligibility criteria will be randomized to receive treatment with one of the two study drugs or placebo. Scheduled visits are to occur as follows: Visit 1 (Screening, Day ≥-28), Visit 2 (Day 1; 24 ±6 hours post-surgery), Visit 3 (Day 4 ±1 day), Visit 4 (Day 8 ±1 day), Visit 5 (Day 15 +1 day) and Visit 6 (Day 21 ±1 day; Exit Visit).

7.2 Study Treatments

RTA 408 Ophthalmic Suspension 0.5% and 1.0% are the active study medications that will be investigated in this study. Placebo (Vehicle of RTA 408 Ophthalmic Suspension) is the control of choice for this study in order to demonstrate the true efficacy of the study drugs. Patients will instill one drop of study medication twice-daily (BID) in the eye that underwent surgery (study eye) in the morning and evening (approximately 12 hours apart) for 14 days.

7.3 Method of Assigning Patients to Treatment Groups

At Visit 1, patients who provide verbal and written informed consent will be assigned a unique 7-digit patient ID, which includes the 4-digit site number plus a unique 3-digit screening number (beginning with 001 within each site). Screening numbers must be assigned in ascending consecutive order. RTA 408 Ophthalmic Suspension 0.5%, RTA 408 Ophthalmic Suspension 1.0% or placebo will be randomly assigned to a sequential list of kit numbers at each site using a 1:1:1 assignment ratio. Sequentially numbered study drug kits will be provided to each investigational site, in accordance with

Statistical Analysis Plan Protocol RTA 408-C-1307

Version 1.0

the site-specific randomized study drug kit list, which consists of sequential 5-digit medication ID numbers. The randomized study drug kit lists will be generated using a complete block design with a block size of 6. Patients who meet all eligibility criteria will be randomized on the first day post-surgery (Visit 2; Day 1) by assignment of the lowest 5-digit study drug kit number available at their investigative site. If a randomized patient is discontinued from the study for any reason, their randomized study drug kit number will not be reassigned. A back-up block of treatments will be available at each site to be used for study treatment replacement.

7.4 Masking and Unmasking

An independent biostatistician who is not otherwise involved in the trial will generate the complete randomized study drug kit list. The patient, Sponsor, Investigators and study staff will be masked during the randomization process and throughout the study.

With each shipment of study drug, sites will receive one emergency unmasking envelope for every study drug kit received, including the back-up study drug kits. The envelopes and kits will both be labeled with the same 5-digit study drug kit number. The envelopes are sealed and contain the unmasked treatment information for the corresponding study drug kit.

Envelopes should be stored in a secured location and should only be opened (i.e., breaking the randomization code for that patient) in the event of a medical emergency, or when knowing the treatment assignment is absolutely necessary for the medical management of the study patient. When possible (i.e., in non-emergent situations), the study sponsor or representative should be notified prior to unmasking study drug. In emergency situations, the investigator must notify the sponsor within 24 hours after determining that it is necessary to unmask the treatment assignment. If the investigator determines that emergency unmasking is necessary, the investigator should identify and retrieve the emergency unmasking envelope for the given patient. The emergency unmasking envelope should be opened by the designated site personnel. The investigator must also indicate in source documents and in the eCRF that the mask was broken and provide the date, time, and reason for breaking the mask. Patients should have their study drug discontinued immediately if treatment assignment is unmasked.

7.5 Schedule of Visits and Assessments

The schedule of visits and assessments is provided below.

Study Parameter	Visit 1 (≥ -28 Days Prior to Surgery)	Visit 2 (Day 1, 24 ± 6 hrs Post- Surgery)	Visit 3 (Day 4 ²)	Visit 4 (Day 8 ²)	Visit 5 (Day 15 ³)	Visit 6 (Day 21 ² , Exit or Early Exit Visit)
Informed Consent/HIPAA	X					
Demographic Data	X					
Medical and Medication	X					

Statistical Analysis Plan Protocol RTA 408-C-1307

Version 1.0

 X^4

X

Visit 6 Visit 1 Visit 2 (Day 21², (≥ -28 (Day 1, Visit 5 Visit 3 Visit 4 24 ± 6 hrs Exit or Days Study Parameter (Day 4²) (Day 8²) (Day 15³) **Early Exit** Prior to Post-Visit) Surgery) Surgery) History Х Х Urine Pregnancy Test (for females of childbearing potential) Review of Inclusion and Χ Х Exclusion Criteria Medical and Medication Х X Х Χ Х History Update Х Х Χ X Ocular Pain Assessment Х Х Х X Х Pin-hole Visual Acuity X X Х Х X Χ Slit Lamp Biomicroscopy Ocular Inflammation Assessment of Anterior Х Х Χ Х Х Х Chamber Cell and Flare (at Slit-lamp Biomicroscopy) Intraocular Pressure X Х Х Х Х Х Assessment Randomization of Study Х Patients Dilated Indirect Х Х Ophthalmoscopic Examination Х Study Drug Instillation Study Drug and Compliance Diary Х Instructions and Dispensation Х Х Х Х Х AE Query Review of Study Drug Х Х Х X Compliance Diary Collection of Study Drug

Exit from Study First study drug dose will be instilled in-office at Visit 2. Patients will instill study drug twice daily at-home in the morning and evening (approximately 12 hrs apart) between study visits, from Day 1 through Day 14.

8. Data Preparation

and Compliance Diary

All reported study data will be recorded on the eCRFs supplied by sing Oracle Remote Data Capture (RDC), version 4.5.3. Only the Principle Investigator and authorized study staff according to the Delegation of Responsibilities log are entitled to make entries in the eCRF.

After data are entered into the clinical study database, electronic edit checks and data review will be performed. All data validation specifications and procedures are detailed in the Data Validation Manual as a separate document. When the database has been declared to be complete and accurate, the database will be locked. Any changes to the database after data have been locked can only be made with the approval of Reata Pharmaceuticals, Inc. and in consultation with Confidential Page 11 of 21 13/FEB/2014

² ±1 Day

In case of early termination or if patient did not return study drug at prior to Visit 5.

Statistical Analysis Plan Protocol

SIGNIFICANTLY DIFFERENT

RTA 408-C-1307 1.0

Version

All analyses outlined in this document will be carried out after the following have occurred:

- All data management requirements are met according to tandard operating procedures, including data entry, performance of edit and validation checks, documentation and resolution of data queries, and database lock with written authorization provided by appropriate
 Sponsor personnel;
- Protocol deviations have been identified and status defined (major/minor deviations);
- Analysis populations have been determined; and
- Randomized treatment codes have been unmasked.

9. Analysis Populations

9.1 Intent-to-Treat Population

The intent-to-treat (ITT) population consists of all patients who are randomized. All data will be included and no patients will be excluded because of protocol violations. The ITT population will be analyzed as randomized and will be used for the efficacy analyses.

9.2 Per Protocol

The Per Protocol (PP) population is a subset of the ITT population and includes patients who remain in the study through Visit 5 (Day 15) with no major protocol violations that would affect the assessment of the primary efficacy endpoints of the study [major protocol violations that would affect the assessment of the primary efficacy endpoints of the study will be determined and documented through a masked review of protocol violations prior to unmasking the study treatment assignments]. Patients without major protocol violations thought to affect the primary efficacy outcome who discontinue the study treatment due to lack of efficacy will be analyzed in the PP analysis with data after study treatment discontinuation imputed as failures for success/failure endpoints and will be imputed using last observation carried forward (LOCF) for the data obtained immediately prior to study medication discontinuation for other endpoints. Otherwise, this population will be analyzed as treated using observed data only for confirmatory analyses.

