10 STATISTICAL HYPOTHESES AND METHODS OF ANALYSES

10.1 Study Populations

10.1.1 Intent-to-Treat Population

The Intent-to-Treat (ITT) population consists of all patients who are randomized. All data will be included and no patients will be excluded because of protocol violations. The ITT population will be analyzed as randomized and will be used for the efficacy analyses.

10.1.2 Safety Population

The Safety population includes all randomized patients who received at least one dose of investigational treatment. The Safety population will be analyzed as treated and will be used for the safety analyses. No data will be excluded for any reason.

10.1.3 Per Protocol Population

The Per Protocol (PP) population is a subset of the ITT population and includes patients who remain in the study through Visit 5 (Day 15) with no major protocol violations that would affect the assessment of the primary efficacy endpoints of the study. Patients without major protocol violations thought to affect the primary efficacy outcome who discontinue the study due to lack of efficacy will be analyzed in the PP analysis with missing data after discontinuation imputed as failures for success/failure endpoints and will be imputed using last observation carried forward (LOCF) for other endpoints. Otherwise, this population will be analyzed as treated using observed data only for confirmatory analyses.

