3.1 Primary Variables

The primary efficacy variables are the following:

- 1. Absence of anterior chamber cells (i.e., score of '0') at Visit 5 (Day 15) for:
 - a. The 1.0% concentration of RTA 408 Ophthalmic Suspension compared to placebo; and
 - b. The 0.5% concentration of RTA 408 Ophthalmic Suspension compared to placebo.
- 2. Absence of pain (i.e., score of '0') at Visit 3 (Day 4) for:
 - a. The 1.0% concentration of RTA 408 Ophthalmic Suspension compared to placebo; to be tested if 1a is statistically significant in favor of the active arm; and
 - b. The 0.5% concentration of RTA 408 Ophthalmic Suspension compared to placebo; to be tested if 1b is statistically significant in favor of the active arm.

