The number and percentage of patients prematurely discontinued from the study and the reasons for study discontinuation will be summarized by treatment group for all randomized patients. The reasons for study discontinuation that will be summarized include: adverse event (AE), protocol violation, lack of efficacy, administrative reasons, sponsor termination of study, voluntary withdrawal, pregnancy and other. A patient listing will be provided that includes the date of and reason for premature study discontinuation.

In addition, patient listings will be provided that include informed consent date, inclusion and exclusion criteria violations, and exclusions from the PP population.

11. Demographic and Baseline Characteristics

The demographic variables collected in this study include age, gender, race, ethnicity and iris color. Patients who record more than one race will be grouped into a single category denoted as multi-racial. Demographic variables will be summarized for each of the analysis populations separately.

Age (years) will be summarized, overall and by treatment, using number of observations, mean, standard deviation, median, minimum and maximum values. Age will also be categorized as follows: <65 years and ≥65 years. Age will be reported in years and calculated using the following formula:

Age = ((informed consent date - date of birth) +1 / 365.25) truncated as an integer

Statistical Analysis Plan Protocol RTA 408-C-1307

Version 1.0

The number and percentage of patients will be presented, overall and by treatment, for age category, gender, race, ethnicity and iris color (for the study eye only).

A patient listing that includes all demographic variables will be provided.

12. Medical History and Concomitant Medications

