14.1 Primary Analysis

The anterior chamber cell grade for all study eyes will be recorded as well as the anterior chamber cell count if the actual number of cells observed is 10 cells or fewer (only white blood cells should be counted; red blood cells and pigment cells should not be counted). The 5-unit grading scale for anterior chamber cells is from 0 to 4 where 0 = 0 cells, 1 = 1 to 10 cells, 2 = 11 to 20 cells, 3 = 21 to 50 cells and 4 = >50 cells.

Ocular pain will be assessed by the patient utilizing a Numerical Pain Rating Scale (NPRS) graded from 0 to 10. Patients will assess the level of pain they are experiencing in the study eye at the time of the assessment.

[figure not shown]
The examiner will ask the patient the following question in reference to Figure 1 and will record the number selected by the subject on the appropriate eCRF.

Statistical Analysis Plan Protocol RTA 408-C-1307

Version 1.0

On a scale of 0 to 10, in which 0 is no pain and 10 is the worst possible or unbearable pain, please mark on the scale the number that best describes the pain or discomfort you are feeling in the operated* eye at this time. The middle of the scale (around 5) can be used to describe "moderate pain".

The proportion of study eyes with absence of anterior chamber cells and the proportion of study eyes with absence of ocular pain will be presented overall and by treatment group using categorical summary statistics, including 90% confidence intervals.

Additionally, 80% and 95% confidence intervals will be constructed around the difference in proportions for each primary outcome using asymptotic normal approximations. Pearson's chi-square tests will be employed for statistical inference testing. Fisher's exact tests and exact confidence intervals will be employed in cases of expected counts less than five.

Additionally, a Cochran-Armitage test will be used to test for trend separately in the proportion of study eyes with absence of anterior chamber cells and the proportion of study eyes with absence of pain with increasing active concentration, using all three treatment groups.

The ITT population will be used for the primary analyses. In addition, confirmatory analyses will be performed on the PP population. The primary analysis variables will be presented in patient listings.

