14.2.1.1	Absence of Anterior Chamber Cells at Day 15 and Ocular Pain at Day 4, Last Observation Carried Forward	Intent-to-Treat
14.2.1.2	Absence of Anterior Chamber Cells at Day 15 and Ocular Pain at Day 4, Observed Data	Intent-to-Treat
14.2.1.3	Absence of Anterior Chamber Cells at Day 15 and Ocular Pain at Day 4, Missing Data Imputed as Failures	Intent-to-Treat
14.2.1.4	Absence of Anterior Chamber Cells at Day 15 and Ocular Pain at Day 4, Observed Data	Per Protocol
14.2.2.1	Absence of Anterior Chamber Cells by Visit	Intent-to-Treat
14.2.2.2	Absence of Anterior Chamber Flare by Visit	Intent-to-Treat
14.2.2.3	Absence of Anterior Chamber Cells and Flare by Visit	Intent-to-Treat
14.2.2.4	Absence of Ocular Pain by Visit	Intent-to-Treat
14.2.3.1	Anterior Chamber Cells Grade by Visit	Intent-to-Treat
14.2.3.1	Anterior Chamber Ceas Grade by Visit Anterior Chamber Flare Grade by Visit	Intent-to-Treat
14.2.3.2	Sum of Anterior Chamber Cells and Flare Grades by Visit	Intent-to-Treat
14.2.3.4	Ocular Pain Score by Visit	Intent-to-Treat
	Summary of Treatment Emergent Adverse Events	Safety
14.3.1.1	Treatment-Emergent Adverse Events by System Organ Class	Safety
14.3.1.2		Safety
14.3.1.3	Treatment-Emergent Adverse Events by System Organ Class and	
14.3.1.4	Relationship to Study Drug	Cofoty
14.3.1.5	Serious Treatment-Emergent Adverse Events by System Organ Class	Safety
14.3.1.6	Treatment-Emergent Adverse Events Leading to Patient Discontinuation by System Organ Class	Safety
14.3.2.1.1	Slit Lamp Biomicroscopy Findings	Safety
14.3.2.1.2	Slit Lamp Biomicroscopy Findings – Shift Table	Safety
14.3.2.2.1	Dilated Indirect Ophthalmoscopic Examination Findings Safe	
14.3.2.2.2	Dilated Indirect Ophthalmoscopic Examination Findings – Shift Table	Safety

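### The single Per Protocol population requires retention to Day 15 even for the Day 4 pain endpoint, so some valid Day 4 scores drop out of the confirmatory pain analysis because of a later event

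*SAP*

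**What the plan says.** The SAP (9.2) describes a PP population that "includes patients who remain in the study through Visit 5 (Day 15) with no major protocol violations". Protocol 10.1.3 has the same condition: "patients who remain in the study through Visit 5 (Day 15) with no major protocol violations". Neither document gives a separate definition for each endpoint.

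The second primary variable is measured much earlier. SAP 3.1 lists it as "Absence of pain (i.e., score of '0') at Visit 3 (Day 4) for" each concentration against placebo.

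The same population serves both endpoints. SAP 14.1 states: "In addition, confirmatory analyses will be performed on the PP population". In the SAP's list of tables (section 20), Table 14.2.1.4, population Per Protocol, is titled "Absence of Anterior Chamber Cells at Day 15 and Ocular Pain at Day 4, Observed Data".

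There is one exception to the retention condition. Under SAP 9.2, patients without a relevant major violation "who discontinue the study treatment due to lack of efficacy will be analyzed in the PP analysis", with outcomes after stopping counted as failures. SAP 10 lists the possible reasons for discontinuation as "adverse event (AE), protocol violation, lack of efficacy, administrative reasons, sponsor termination of study, voluntary withdrawal, pregnancy and other". Only lack of efficacy receives the exception.

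**The concern.** The pain endpoint is complete once the Visit 3 score is recorded. Whether the patient is still in the study 11 days later says nothing about adherence up to Day 4 or about the validity of that score. Requiring retention to Visit 5 makes inclusion in the Day 4 analysis depend on a later event, and the reason recorded for that event decides whether the patient stays in.

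Both the event and the reason could depend on treatment and on how the eye felt at Day 4. If so, the PP comparison of Day 4 pain carries a selection effect unrelated to protocol adherence. The PP analysis is there to be compared with the ITT result. If the two differ, the reader could not tell whether the cause is protocol violations, which is the purpose of a PP set, or the removal of later leavers.

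**Working it through.** **1. Who is excluded.** Take three patients, each compliant, each with a valid Visit 3 pain score, and each with a change on Day 10.

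| Patient | What happens on Day 10 | In the PP set for Day 4 pain? |
|---|---|---|
| A | Leaves the study for an adverse event or by withdrawing | No: not in the study at Visit 5 |
| B | Stops treatment for lack of efficacy | Yes, by the exception; the observed Day 4 score stands because it precedes stopping |
| C | Stops drug for another reason but attends through Visit 5 | Meets the retention condition, and is in unless a major violation is found |

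The difference in treatment is between A and B. C shows that the trigger is leaving the study, not stopping drug.

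**2. How many patients could be affected.** The Protocol synopsis and 5.1 give 105 enrolled (35 per arm) to complete 93 (31 per arm). Check: 3 × 35 = 105 and 3 × 31 = 93. Implied loss: 1 − 31/35 = 11.4%, or 4 per arm and 12 in total. Completion is defined through Visit 6 (Protocol 8.6.1), so these 4 also cover losses before Day 4, losses after Visit 5 and departures for lack of efficacy. Four per arm is thus a practical upper bound under the planned loss, and the expected number is lower. The sample-size text is blank in the public copy, so no stated power figure can be reproduced.

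**3. What it could do to the estimate.** The documents give no Day 4 pain rates, so those below are assumed. The test is the one-sided Pearson statistic in z form: z = (p₁ − p₂) / √[p(1 − p)(1/n₁ + 1/n₂)], where p is the pooled proportion. The plan's level is 0.10 one-sided.

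Worked line, 18/35 against 13/35: p = 31/70 = 0.4429, standard error 0.1187, difference 0.1429, z = 1.203, p-value 0.114.

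| Day 4 pain-free, active vs placebo | Leavers removed | After removal | Difference (points) | One-sided p |
|---|---|---|---|---|
| 18/35 vs 13/35 | none | unchanged | 14.3 | 0.114 |
| | 1 active, in pain | 18/34 vs 13/35 | 15.8 | 0.094 |
| | 4 active, in pain | 18/31 vs 13/35 | 20.9 | 0.045 |
| 21/35 vs 14/35 | none | unchanged | 20.0 | 0.047 |
| | 1 active, in pain | 21/34 vs 14/35 | 21.8 | 0.035 |
| | 1 active, pain-free | 20/34 vs 14/35 | 18.8 | 0.059 |
| | 4 active, in pain | 21/31 vs 14/35 | 27.7 | 0.012 |
| | 4 active, pain-free | 17/31 vs 14/35 | 14.8 | 0.114 |
| | 4 per arm, all in pain | 21/31 vs 14/31 | 22.6 | 0.037 |

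Four leavers from one arm move the difference by +6.6 (20.9 − 14.3), +7.7 (27.7 − 20.0) or −5.2 (14.8 − 20.0) points. One leaver moves it by 1.2 to 1.8 points. Losses equal in number and alike in pain status move it by 2.6 points. Equal numbers alone do not guarantee a small shift: if the four active leavers are in pain and the four placebo leavers are pain-free, 21/31 vs 10/31 gives 35.5 points. That is an extreme arrangement.

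**4. Whether another provision covers it.** The masked review in SAP 9.2 classifies protocol violations; it does not touch the retention condition. SAP 17 discloses a change in PP imputation for patients stopped for lack of efficacy and is silent on Visit 5 retention for the Day 4 endpoint.

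**The case against.** The case against giving this weight is strong, and most of it stands.

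- **No decision rests on the PP result.** ITT is the primary population, and observed Day 4 scores stay in it. Study success and the gate to the pain test are set by the primary tests alone. A reader might infer from the rows that cross 0.10 that a trial conclusion could change. The plan attaches no consequence to the PP p-value: where the ITT pain result is p = 0.114, the pain test has failed whatever PP shows.
- **The scores are not lost.** Table 14.2.1.2, the ITT observed-data analysis, includes these patients' Day 4 scores. SAP 10 also reports population counts and discontinuations by reason and arm, with a listing of PP exclusions, so lopsided exclusion would be visible.
- **The trigger is narrow.** Protocol 8.6.2 encourages patients who stop drug to stay in the study, and those given escape medication are to remain. Only departures between Visits 3 and 5 matter.
- **The direction is not known.** A reader might infer that the rule favours active treatment, because adverse-event leavers would be active-arm patients with discomfort. The pain question does cover discomfort, and irritation was seen in a rabbit study at four-times-daily dosing. But that finding was reversible and absent in monkeys, and this is the first clinical study of the product. The documents do not support a claim that reasons for leaving will differ by arm.

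What remains is that a planned confirmatory analysis of a primary endpoint selects patients on a post-endpoint event, and nothing else in the plan corrects this.

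**Conclusion.** The point holds, at minor severity. The Visit 5 condition has no rationale for a Day 4 endpoint, and it excludes compliant patients with valid scores who leave between Visits 3 and 5 for reasons other than lack of efficacy. The effect is confined to the interpretation of the PP pain result.

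Under the assumed rates the shift is roughly 5 to 8 points if all four planned non-completers in one arm leave in that window with the same pain status, in either direction, and 1 to 2 points for a single leaver. These sizes rest on assumed response rates, on the planned loss of about 4 of 35 per arm being a fair ceiling, and on losses falling in one arm. With an endpoint-specific PP set, no patient is excluded from Day 4 pain merely for leaving after Visit 3.

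**What to change.** In SAP 9.2 and Protocol 10.1.3, define the PP population by endpoint:

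- **Day 4 pain:** in the study through Visit 3, with no major violation up to Visit 3 that affects the pain assessment, whatever the later disposition.
- **Day 15 anterior chamber cells:** the present definition.
- **Both:** keep the existing lack-of-efficacy imputation rule.

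Show both PP denominators in Table 14.2.1.4. Carry the second flag into the population summary (Table 14.1.1), PP disposition (14.1.2.2), PP demographics (14.1.4.3) and the listing of exclusions (16.2.3). If the Protocol is not amended, record the change in SAP 17.

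The cost is a sentence or two, one more flag in the analysis dataset and a small amount of table programming. No new data are needed, and the masked review of violations is already planned; it would also have to date each violation relative to Visit 3.
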